7.2. Secondary Variables

NIHSS

The NIH Stroke Scale assesses neurologic deficit and is a 15 items scale that covers the level of consciousness, gaze, visual fields, facial palsy, motor functions, limb ataxia, aphasia, dysarthria and extinction and inattention. The NIHSS is observer-rated and takes 5-8 min to complete. Items have 3- to 5-point response scales, scored from 0 to 4 with higher score indicative of more severe disability. In case of patient death, the worst score possible will assigned. The NIHSS will be used to assess the severity of the stroke at baseline as well as in the follow-up examinations as a measure of neurological function deficit.

modified Rankin Scale

The Modified Rankin Score is a functional outcome scale measuring global outcome. It is used for grading the outcome and the level of disability after a stroke. The Modified Rankin Score is a 7-point ordinal scale with a score of 0 indicative of no residual symptoms at all and the worst possible score of 6 which is assigned in case of death. The Modified Rankin Scale is observer rated and takes about 5 min to complete.

Barthel Index

The Barthel Scale/Index (BI) is an ordinal scale used to measure performance in activities of daily living (ADL). Ten variables describing ADL and mobility are scored, a higher number being a reflection of greater ability to function independently following hospital discharge. Time taken and physical assistance required to perform each item are used in determining the assigned value of each item. The Barthel Index measures the degree of assistance required by an individual on 10 items of mobility and self care ADL.

7.3. Further Variables

Neurological and physical examinations will be performed according to hospital standard procedures and will be recorded in the CRF.

Anamnestic data will be collected according to standard hospital procedures and the medical history will be documented in the CRF.

Vital signs including systolic and diastolic blood pressure, heart rate, respiratory rate and body temperature will be measured and documented in the CRF.

Standard laboratory parameters will be analysed according to standard procedures.

Information on all concomitant treatments and medications will be collected and documented.

Information on adverse events and patient safety will be collected in the CRF.

7.4. Source Documents

The following definitions of source documents shall apply:

Variable	Source document
Informed consent form	Patient File
Patient's demographic data such as sex, age, weight, indication, concomitant diseases, medical history, medication (history and concomitant), physical examination etc.	Patient File
Outcomes Variables	Patient File
Adverse Events	Patient File

8. ASSESSING AND REPORTING OF ADVERSE EVENTS

Throughout the course of the clinical study particular attention is paid to the Adverse Events and Adverse Drug Reactions mentioned below.

8.1. Adverse Events (AE)

A Serious/Adverse Event (S/AE) is any untoward medical occurrence in a patient or clinical investigation subject administered a pharmaceutical product and which does not necessarily have a causal relationship with this treatment. An AE can therefore be any unfavourable and unintended sign (including an abnormal laboratory finding), symptom, or disease temporally associated with the use of an Investigational Product, whether or not related.

8.2. Adverse Drug Reaction (ADR)

All untoward and unintended responses to an Investigational Product related to any application / dose administered. The phrase "responses to an Investigational Product" means having a reasonable causal relationship as judged by either the Investigator or the Coordinator. The expression reasonable means to convey in general that there is evidence or argument to suggest a causal relationship.

Regarding marketed Investigational Products: a response to a product which is noxious and unintended and which occurs at applications normally used in man for prophylaxis, diagnosis, or therapy of diseases or for modification of physiological function.

8.2.1. Serious Adverse Event or Serious Adverse Reaction (SAE/SAR)

Serious Adverse Events will due to the underlying constitution of the patient be considered for AE documentation. Serious Adverse Drug Reactions will be dealt with as described below.

Expedited Reporting is required if the following criteria apply (ICH E2A):

- 1. Serious
- 2. Unexpected
- 3. Reasonable causal relationship to study treatment.

An Adverse Drug Reaction is considered serious if it:

- Results in Death
- Is life threatening
- Requires additional inpatient hospitalization or prolongation of existing
- hospitalization
- Results in persistent or significant disability / incapacity
- Results in a congenital anomaly or birth defect
- Other medically significant event that requires immediate medical or surgical
- Intervention

Unexpected means:

• Not consistent with Investigators Brochure or SmPC

Causal Relationship means:

- There are facts/evidence to suggest a causal relationship
- As judged by the reporting health care professional to have reasonable suspected causal relationship

NOTE

Death: is the outcome of an Adverse Event. The event to be reported comprehensively is the medical condition leading to death, e.g. underlying disease, accident.

Life-threatening: in the definition of a Serious Adverse Event or Adverse Reaction refers to an event in which the patient was at risk of death at the time of the event; it does not refer to an event which hypothetically might have caused death if it was more severe.

Medical judgement should be exercised in deciding whether an Adverse Event / Reaction is serious in other situations. Important Adverse Events / Reactions that are not immediately life-threatening or do not result in death or hospitalisation but may jeopardise the patient or may require intervention to prevent one of the other outcomes listed in the definition above, should also be considered serious.

8.3. Suspected Expected Serious Adverse Reaction (SESAR)

Any adverse reaction that is classed in nature as serious and which is consistent with the available information on the medicinal product in question set out in the SmPC

8.4. Suspected Unexpected Serious Adverse Reaction (SUSAR)

Any adverse reaction that is classed in nature as serious and which is **not** consistent with the available information on the medicinal product in question set out in the SmPC

8.5. Recording of Adverse Events

All adverse events, according to previously provided definitions, whether they are considered serious or not will be documented and were applicable reported.

The Investigator must report in detail all adverse signs and symptoms which are either volunteered by patients or observed during or following the course of Investigational Product administration on the appropriate CRF page.

Included in the description should be the nature of the sign or symptom; the date of onset; date of resolution (duration); the severity / intensity; the relationship to study treatment or other therapy; the action taken (if any), and the outcome.

8.5.1. Definition of Adverse Event intensity

Intensity	Definition	
Mild	Patient is aware of signs and symptoms, but they are easily tolerated	
Moderate	Signs / symptoms cause sufficient discomfort to interfere with usual activities	
Severe	Patient is incapable to work or perform usual activities	

8.5.2. Definition of Adverse Event causality

On the basis of the WHO-UMC system for standardised case causality assessment (www.who-umc.org), the following categories are used to describe the degree of causality (all points should be reasonably complied with):

Definite

- Event or laboratory test abnormality, with plausible time relationship to drug intake

- Cannot be explained by disease or other drugs
- Response to withdrawal plausible (pharmacologically, pathologically)
- Event definitive pharmacologically or phenomenologically (i.e. an objective

and specific medical disorder or a recognised pharmacological phenomenon)

- Re-challenge satisfactory, if necessary

Probable

- Event or laboratory test abnormality, with reasonable time relationship to drug intake

- Unlikely to be attributed to disease or other drugs
- Response to withdrawal clinically reasonable (for details refer to WHO-UMC)
- Re-challenge not required

Possible

- Event or laboratory test abnormality, with reasonable time relationship to drug intake

- Could also be explained by disease or other drugs

- Information on drug withdrawal may be lacking or unclear

Unlikely

- Event or laboratory test abnormality, with a time to drug intake that makes a relationship improbable (but not impossible)

- Disease or other drugs provide plausible explanations

Not related

The event does not follow a reasonable temporal sequence from administration of the IMP and is clearly related to other factors, such as clinical state, therapeutic intervention or concomitant therapy.

Not assessable

- Report suggesting an adverse reaction
- Cannot be judged because information is insufficient or contradictory
- Data cannot be supplemented or verified

All cases judged by any or both assessors as having a "reasonable causal relationship" to the IMP qualify as ADR. This corresponds to the categories "definite", "probable" and "possible".

8.6. Reporting Serious Adverse Events

All Serious Adverse Reactions and all Unexpected Serious/Adverse Reactions with at least a suspicion of causal relationship to the investigational product must be reported to the Coordinator within 24 hours (one working day) of the Investigator becoming first knowledge. Preference in the reporting is the SAE report by e-mail at [contact].

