8.7. Exemption from expedited reporting

Not applicable

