9. STUDY SCHEDULE

9.1. Procedures at Each Visit

Visit 1 – Baseline – 3-5 days post-stroke (Study Day 1)

- Demographics
- Medical history
- Western Aphasia Battery
- NIHSS

Visit 2 – Study Day 30 ± 3

- Western Aphasia Battery
- NIHSS
- Barthel Index
- modified Rankin Scale
- Adverse Events (AE)
- Severe Adverse Events (SAE)

Visit 3 – Study Day 60 ± 3

- Western Aphasia Battery
- NIHSS
- Barthel Index
- modified Rankin Scale
- Adverse Events (AE)
- Severe Adverse Events (SAE)

Visit 4 - Study Day 90 ± 3

- Western Aphasia Battery
- NIHSS
- Barthel Index
- modified Rankin Scale
- Adverse Events (AE)

• Severe Adverse Events (SAE)

Treatment cycles

Treatment Cycle 1 – 30 ml Cerebrolysin/saline and ST for 2 x 5 days (2 weeks)

Study days 1 – 14 30ml Cerebrolysin/saline i.v. 1h Speech Therapy

Treatment Cycle 2 – 30 ml Cerebrolysin/saline and ST for 2 x 5 days (2 weeks)

Study days 29-42 30ml Cerebrolysin/saline i.v. 1h Speech Therapy

Treatment Cycle 3 – 30 ml Cerebrolysin/saline and ST for 2 x 5 days (2 weeks)

Study days 57-70 30ml Cerebrolysin/saline i.v. 1h Speech Therapy

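### Serious adverse events the investigator does not attribute to the drug have no deadline for reaching the Coordinator, so the either-assessor causality rule cannot work in time; the SAE label and the reporting limit also conflict

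*Protocol*

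**What the plan says.** **Who decides causality.** Protocol section 8.2 treats a response as related if either the Investigator or the Coordinator finds a reasonable causal relationship. Section 8.5.2 repeats this: "All cases judged by any or both assessors as having a" reasonable causal link qualify as reactions. It maps that link to the ratings definite, probable and possible.

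**What is reported promptly.** Section 8.6 is headed as the section on reporting serious adverse events, but its duty is narrower: "All Serious Adverse Reactions and all Unexpected Serious/Adverse Reactions with at least a suspicion of causal relationship" go to the Coordinator, and the limit runs from the Investigator's first knowledge. For expedited reporting, section 8.2.1 describes causality as judged by the reporting health care professional.

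**What happens to the rest.** Section 8.2.1 states: "Serious Adverse Events will due to the underlying constitution of the patient be considered for AE documentation". Section 8.5 has all adverse events, serious or not, documented on the CRF. Section 14.7.1 asks for completed, signed CRFs to be open to the monitor within two weeks of each patient's completion. Section 13.2 provides monitoring visits at regular intervals without fixing the interval.

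**The label.** The synopsis and section 9.1 list "Severe Adverse Events (SAE") as what is collected. Section 8 expands the same abbreviation as Serious. Section 8.5.1 defines Severe as the top intensity grade: "Patient is incapable to work or perform usual activities".

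**The time limit.** Section 8.6 says such reactions "with at least a suspicion of causal relationship to the investigational product must be reported to the Coordinator within 24 hours (one working day").

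**The concern.** A rule that lets either of two assessors establish causality exists to catch events that the first assessor dismisses. Here the first assessor's opinion decides whether the second is told promptly, so the rule gives least protection where it is most needed. If the Coordinator would have judged a serious event to be related, the protocol gives no assurance that this happens while the patient is still being treated, or in time for expedited reporting.

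The label is a separate matter. Safety is a stated secondary objective and SAE is one of its two named variables. If a site follows the visit list and the intensity table, it may record severe events. If it follows section 8, it will record serious ones. These are different sets: a severe event need not be serious, and a serious one need not be graded severe.

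**Working it through.** The protocol gives no figure to reproduce here. The check is a comparison of sections plus simple date arithmetic.

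**Step 1: follow a serious event by the investigator's rating.**

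| Investigator's rating (8.5.2) | A reaction on that rating alone? | Dated route to the Coordinator |
|---|---|---|
| Definite, probable, possible | Yes | Section 8.6: 24 hours / one working day |
| Unlikely, not related, not assessable | No, unless the Coordinator judges otherwise | None in 8.6; CRF open to the monitor two weeks after patient completion (14.7.1) |

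The second row is circular. Under 8.2 the event becomes a reaction, and so reportable under 8.6, once the Coordinator judges it causal. But nothing in 8.6 brings it to the Coordinator for that judgement. A later reclassification also cannot meet the 8.6 limit, because that limit runs from the Investigator's first knowledge. Not assessable is the least clear of the three ratings: 8.5.2 describes it as a report suggesting a reaction, yet leaves it out of the list of ratings that count as one.

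**Step 2: how late the dated route is.** Inputs: Visit 4 at Study Day 90 ± 3 (9.1); CRF within 14 days of completion (14.7.1); third treatment cycle ends on Day 70 (9.1). Assume an event on Study Day 1, a patient who completes at Visit 4, and no earlier monitoring visit that finds the event.

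- CRF due, Visit 4 on the nominal day: 90 + 14 = Day 104.
- CRF due, Visit 4 at the end of its window: 93 + 14 = Day 107.
- Delay from Day 1: 104 − 1 = 103 days to 107 − 1 = 106 days. Divided by 7, that is 14.7 to 15.1 weeks, against 24 hours for a suspected reaction.
- Relative to the end of treatment: 104 − 70 = 34 days to 107 − 70 = 37 days after the third cycle ends.

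**Step 3: the label.** Severe is used once in the synopsis safety variables, three times in the synopsis visit schedule (Visits 2 to 4) and three times in section 9.1: 1 + 3 + 3 = 7. Section 8 consistently uses Serious for SAE.

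**Step 4: the limit.** Assume that working days exclude the weekend and there is no public holiday. Knowledge gained on a Friday then allows until the same hour on Monday: 3 × 24 = 72 hours. The two expressions in 8.6 agree only when the next day is a working day.

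**The case against.** The strongest reply is that the protocol's threshold for suspicion is low. Under 8.5.2, an event with reasonable timing that could also be explained by disease is rated possible, and possible counts as a reaction. With treatment cycles over Days 1–14, 29–42 and 57–70, many serious events will have plausible timing and will be reportable at once, even if the stroke could explain them. This stands, and it narrows the gap to the three ratings in the lower row of the table. It does not close the gap, because the investigator still assigns the rating alone.

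Second, a reader might infer that these events never reach the Coordinator, or that the either-assessor rule cannot work at all. The documents do not support that. Section 8.5 records every adverse event, 9.1 collects them at Visits 2 to 4, 8.8 follows them up, and monitors verify source data. Nothing forbids earlier notification. What is missing is a deadline.

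Third, a reader might see a contradiction in section 8.7, where "Exemption from expedited reporting" is marked not applicable. There is none: 8.2.1 limits expedited reporting to events that are serious, unexpected and causally related, so unrelated events need no exemption.

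Fourth, the seriousness list in 8.2.1 is introduced for drug reactions, and a reader might conclude that serious events are undefined. The section heading and the note below the list refer to events as well as reactions, so that reading fails.

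Fifth, the label can be called a slip, since section 8 expands the abbreviation correctly and section 8.5 records intensity separately. It probably is a slip, but seven repetitions in the places that define what is collected warrant correction. It has no bearing on the causality rule.

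Finally, prompt reporting would bring the Coordinator blinded cases, not a difference between arms, because unblinding follows database closure (4.4). That stands. The gain is timely assessment of individual cases. How events are compared between arms is for the statistical analysis plan and is not at issue here.

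**Conclusion.** The point holds in this form: the either-assessor rule in 8.2 and 8.5.2 cannot work in time for expedited reporting of serious events that the investigator rates unlikely, not related or not assessable. Sections 8.6 and 8.2.1 give those events no prompt route to the second assessor. In the worst case the only dated route runs to about Day 104 to 107 for a Day 1 event, after treatment has ended. That figure assumes the patient completes at Visit 4 and no monitoring visit intervenes; because the visit interval is not fixed, the typical delay cannot be stated.

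The share of serious events affected cannot be stated either. The protocol gives neither an expected rate of serious events nor the proportion investigators would leave unsuspected, and the low threshold for possible keeps that proportion down by an unknown amount. The conclusion needs neither number.

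The Severe/Serious conflict and the two time limits are independent wording defects. Both are real on the text and should be corrected at the same time. None of the three touches the primary variable.

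**What to change.** - **Section 8.6:** require all serious adverse events, whatever the investigator's causality rating, to be reported to the Coordinator, who then applies the either-assessor rule.
- **Section 8.2.1:** reconcile the sentence that sends serious events to adverse event documentation, and the reference to the reporting professional's judgement, with the revised 8.6 and with 8.2 and 8.5.2.
- **Time limit in 8.6:** reconcile 24 hours and one working day to a single limit.
- **Synopsis and section 9.1:** replace Severe by Serious in all seven expansions of SAE, check that the CRF label agrees, and keep intensity as a separate attribute of every adverse event.

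The cost is a protocol amendment, any matching CRF label change, and a modest number of extra SAE forms among 120 patients. The design, sample size and primary variable are unaffected.

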8.7. Exemption from expedited reporting

Not applicable

8.8. Adverse Event/Reaction follow-up procedures

Adverse Events/ Reactions will be followed up throughout the course of the clinical study and any changes will be recorded in the CRF.

9. STUDY SCHEDULE

9.1. Procedures at Each Visit

Visit 1 – Baseline – 3-5 days post-stroke (Study Day 1)

- Demographics
- Medical history
- Western Aphasia Battery
- NIHSS

Visit 2 – Study Day 30 ± 3

- Western Aphasia Battery
- NIHSS
- Barthel Index
- modified Rankin Scale
- Adverse Events (AE)
- Severe Adverse Events (SAE)

Visit 3 – Study Day 60 ± 3

- Western Aphasia Battery
- NIHSS
- Barthel Index
- modified Rankin Scale
- Adverse Events (AE)
- Severe Adverse Events (SAE)

Visit 4 - Study Day 90 ± 3

- Western Aphasia Battery
- NIHSS
- Barthel Index
- modified Rankin Scale
- Adverse Events (AE)

• Severe Adverse Events (SAE)

Treatment cycles

Treatment Cycle 1 – 30 ml Cerebrolysin/saline and ST for 2 x 5 days (2 weeks)

Study days 1 – 14 30ml Cerebrolysin/saline i.v. 1h Speech Therapy

Treatment Cycle 2 – 30 ml Cerebrolysin/saline and ST for 2 x 5 days (2 weeks)

Study days 29-42 30ml Cerebrolysin/saline i.v. 1h Speech Therapy

Treatment Cycle 3 – 30 ml Cerebrolysin/saline and ST for 2 x 5 days (2 weeks)

Study days 57-70 30ml Cerebrolysin/saline i.v. 1h Speech Therapy

9.2. Assessment of Compliance

Compliance will be documented by recording the date and time of the administration in the CRF. The number of IV infusions actually administered to each patient will be calculated as the percentage of the total number of IV infusions planned per protocol and will provide a measure of treatment compliance.

9.3. Risk assessment and Precautionary Measures

The investigational medicinal product is in clinical use for many years and has demonstrated a very benign safety profile.

The safety information for the IMP is provided in the SmPC in Appendix 1.

10. STUDY AND TREATMENT DURATION

Study/Treatment start: 06 / 2020

Study/Treatment end: 06 / 2022

11. STATISTICS

The this is an exploratory study and the statistical analysis will be defined in a statistical analysis plan which will be finalized before unblinding of the study data.

12. ACCESS TO SOURCE DATA / DOCUMENTS

The Investigator will permit study-related monitoring, audits, IRB / IEC review and regulatory inspections, providing direct access to primary patient data (i.e. source data) which supports the data on the CRFs for the study, i.e. general practice charts, appointment books, original laboratory records etc.

12.1. Source Data

Source data are defined as all information in original records and certified copies of original records of clinical findings, observations or other activities in a clinical study necessary for the reconstruction and evaluation of the study. Source data are contained in source documents (original records or certified copies).

12.2. Source Documents

Source documents are defined as original documents, data and records (e.g. hospital records, clinical and office charts, laboratory notes, memoranda, patient diaries or evaluation check lists, pharmacy dispensing records, recorded data from automated instruments, copies or manuscripts certified after verification as being accurate copies, microfiches, photographic negatives, microfilm or magnetic media, patient files, records kept at pharmacy, at the laboratories and at medico technical departments involved in clinical study).

12.3. Direct Access

Direct access is defined as the permission to examine, analyse, verify and reproduce any records and reports that are important to evaluation of a clinical study. Any party (e.g. domestic and foreign regulatory authorities, the Coordinator and / or authorised representatives of the Coordinator such as monitors and auditors) with direct access should take all reasonable precautions within the constraints of the applicable regulatory

requirements to maintain the confidentiality of patient identities and Coordinator proprietary information.

